5.2 Extent of exposure

Exposure will be summarised based on the SAF. For each treatment group, the summary will include the total patient years of exposure, the total patient weeks of exposure and the exposure time, based on the categories ‘< 16 weeks’, ‘16-24 weeks’, and ‘> 24 weeks’. For each treatment group, the summary will also include the total patient years of observation, beginning from the date of randomisation and ending at the date of last contact. Subjects will be considered exposed to IMP within 5 half-lives after the most recent date of IMP administration with half-lives assumed to be as described in [Panel 8](#). Exposure time will be truncated at the end of observation, i.e. at the date of last contact.

Panel 8. Assumed half-lives for investigational medicinal products

IMP	Assumed half-life	Rationale for assumption
Brodalumab Trade name: Kyntheum®	10.9 days	According to (1), “(...) the estimated half-life of brodalumab was 10.9 days at steady-state after every other week subcutaneous dose of 210 mg”
Guselkumab Trade name: Tremfya®	16.5 days	According to (2), “Mean half-life ($T_{1/2}$) of guselkumab was approximately 17 days in healthy subjects and approximately 15 to 18 days in patients with plaque psoriasis across studies”. Based on this, the average of 15 days and 18 days will be the assumed half-life.
Placebo 1.0 mL (dummy 1 to mimic guselkumab)	0.0 days	According to the CTP Panel 6, “The placebo solution (...) does not contain any active substance”.
Placebo 1.5 mL (dummy 2 to mimic brodalumab)	0.0 days	According to the CTP Panel 6, “The placebo solution (...) does not contain any active substance”.

Abbreviations: CTP = clinical trial protocol; IMP = investigational medicinal product. **Notes:** The described IMPs refer to those identified in CTP Panel 6.

THIS DOCUMENT CONTAINS CONFIDENTIAL INFORMATION AND MUST NOT BE COPIED OR MADE AVAILABLE TO ANY THIRD PARTY WITHOUT THE PRIOR WRITTEN CONSENT OF THE LEO PHARMA GROUP

The cumulated number of doses administered to each subject will be determined and summarised descriptively. The same summarisation will be done for the cumulated number of active doses administered to each subject. For subjects who withdraw from the trial, are lost to follow-up, or permanently discontinue IMP, their cumulated number of doses will be calculated up until the time of withdrawal/loss to follow-up/permanent discontinuation of IMP.

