13.1 Definition and classification of adverse events

AEs and SAEs are defined in [Appendix 1](#).

Classification of AEs in terms of severity, causality, and outcome is defined in [Appendix 2](#). Causality assessment will be made for all IMPs (brodalumab, guselkumab, and dummies).

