1.2 Trial design

This trial is a phase 4, randomised, blinded (subject and assessor), parallel-group, multi-site, clinical trial. The trial is designed to evaluate the efficacy and safety of standard administration of brodalumab compared with standard administration of guselkumab for the treatment of moderate-to-severe plaque psoriasis in adult subjects with inadequate response to ustekinumab. A schematic of the trial design is provided in [Panel 3](#).

Panel 3: Trial design

Abbreviations: Q2W = every 2 weeks; Q8W = every 8 weeks; W = week, N = number of subjects.

THIS DOCUMENT CONTAINS CONFIDENTIAL INFORMATION AND MUST NOT BE COPIED OR MADE AVAILABLE TO ANY THIRD PARTY WITHOUT THE PRIOR WRITTEN CONSENT OF THE LEO PHARMA GROUP

Eligible subjects will be randomised to either brodalumab or guselkumab treatment regimen as described below. Randomisation will be stratified by body weight (≤ 100 kg, > 100 kg).

Arm 1 (brodalumab + dummy 1):

- Brodalumab 210 mg (1.5 ml) subcutaneously at Weeks 0, 1, 2, and then Q2W until the end of trial (last administration of brodalumab at Week 26).
- Dummy 1 (placebo 1.0 ml) subcutaneously at Weeks 0, 4, and then every 8 weeks (Q8W) until the end of trial (last administration of dummy 1 at Week 20).

Arm 2 (guselkumab + dummy 2):

- Guselkumab 100 mg (1.0 ml) subcutaneously at Weeks 0, 4, and then Q8W until the end of trial (last administration of guselkumab at Week 20).
- Dummy 2 (placebo 1.5 ml) subcutaneously at Weeks 0, 1, 2, and then Q2W until the end of trial (last administration of dummy 2 at Week 26).

Discontinuation and withdrawal

A subject may withdraw from the trial (prior to first dose or during the treatment period) or permanently discontinue trial treatment at any time if the subject, the investigator, or LEO Pharma considers that it is not in the subject's best interest to continue.

To obtain the most representative efficacy and safety evaluation of brodalumab in the target population, the subject will be asked to remain in the trial and complete all the remaining visits and assessments after permanent discontinuation of IMP. It is key to assess the efficacy status of each subject at the planned primary endpoint visit (Week 16) irrespective of whether the subject has discontinued IMP or not. Therefore, the permanent discontinuation of IMP is evaluated as a separate occurrence that does not necessitate withdrawal from the trial.

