5.6.1 Adverse events

AEs will be coded during the course of the trial according to Medical Dictionary for Regulatory Activities (MedDRA). AEs will be presented by preferred term (PT) and primary system organ class (SOC).

For AEs, missing values will be treated as missing, except for causality, intensity, seriousness, onset date and outcome of AEs. A worst-case approach will be used: if causality is missing, the AE will be regarded as related to the IMP; if the intensity of an AE is missing, the AE will be regarded as severe; if seriousness is missing, the AE will be regarded as serious; if onset date is missing, it will be assumed to be the first day of administration of IMP; if outcome is missing, and no date of outcome is present, the outcome is regarded as ‘not recovered’.

THIS DOCUMENT CONTAINS CONFIDENTIAL INFORMATION AND MUST NOT BE COPIED OR MADE AVAILABLE TO ANY THIRD PARTY WITHOUT THE PRIOR WRITTEN CONSENT OF THE LEO PHARMA GROUP

Treatment-emergent AEs will be summarised; however, all AEs recorded during the course of the trial will be included in subject data listings. An event will be considered treatment-emergent if the onset occurred after the first administration of IMP or if the event started prior to the first administration of IMP and worsened in severity after the first administration of IMP. Please refer to the ADRG regarding details on imputation of treatment-emergent flagging when timing information is missing. The tabulations described in the following will only include the treatment-emergent events reported prior to or at the Week 28 visit. In each of the tabulations, AEs are defined by MedDRA preferred terms within primary SOC. Tabulations of treatment-emergent AEs will be presented for the following 2 scenarios:

- ‘While exposed to IMP’, defined as AEs occurring within 5 half-lives after the most recent date of IMP administration.
- ‘While in trial’, defined as all AEs observed during the duration of the trial, beginning from the date of randomisation.

An overall summary of the number and percentage of subjects reporting the event, along with the number of events and the event rate per 100 subject-years for any treatment-emergent AEs, deaths, SAEs, AEs leading to permanent discontinuation of IMP or withdrawal from trial, treatment-related AEs, and severe AEs will be presented. An overall graphically summary of AEs by seriousness, severity, outcome and permanent discontinuation of IMP will be presented using histograms.

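### The SAP's exposure window does not say that dummy injections are disregarded, and taken literally it removes three quarters of a guselkumab completer's exposed time

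*SAP*

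**What the plan says.** SAP 5.2 defines exposure in one sentence: "Subjects will be considered exposed to IMP within 5 half-lives after the most recent date of IMP administration". The half-lives come from Panel 8, and exposure time is cut off at the date of last contact. SAP 5.6.1 repeats the rule for the 'while exposed to IMP' adverse event tables, "defined as AEs occurring within 5 half-lives after the most recent date of IMP administration", and protocol 14.3.9.1 has the same definition.

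Panel 8 has four rows: brodalumab at 10.9 days, guselkumab at 16.5 days, and dummy 1 and dummy 2 at 0.0 days each. All four stand in the IMP column, and the note adds: "The described IMPs refer to those identified in CTP Panel 6". Protocol 13.1 also treats the dummies as IMPs: "Causality assessment will be made for all IMPs (brodalumab, guselkumab, and dummies").

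The distinction between active and dummy is made elsewhere in SAP 5.2, but only for dose counts: "The same summarisation will be done for the cumulated number of active doses administered to each subject".

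For the guselkumab arm, SAP 1.2 schedules the active drug at Weeks 0, 4, 12 and 20, together with "Dummy 2 (placebo 1.5 ml) subcutaneously at Weeks 0, 1, 2, and then Q2W until the end of trial", the last dummy being at Week 26.

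**The concern.** The rule looks for the latest IMP date, and in this trial a dummy injection is an IMP administration. If the most recent IMP is a dummy, its window is 5 × 0.0 = 0 days, so a subject who still has guselkumab on board counts as unexposed until the next guselkumab dose. The brodalumab arm has no visit at which only a dummy is given, so the effect falls on one arm.

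The window drives total exposure time, the three exposure-time categories, and the 'while exposed to IMP' summaries of adverse events, AESIs (SAP 5.6.2), C-SSRS and PHQ-8 (protocol 14.3.9.5 and 14.3.9.6, which SAP 5.6.6 and 5.6.7 adopt). Comparing the safety of the two drugs is a stated objective. If the window behaved differently by arm, those tables would compare unlike periods.

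**Working it through.** **Inputs**

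- Guselkumab half-life (SAP Panel 8): "Based on this, the average of 15 days and 18 days will be the assumed half-life". (15 + 18) / 2 = 16.5 days, which reproduces the plan's figure.
- Brodalumab half-life (SAP Panel 8): the cited source says "the estimated half-life of brodalumab was 10.9 days at steady-state after every other week subcutaneous dose of 210 mg".
- Dummy half-life (SAP Panel 8): 0.0 days.
- Window lengths: guselkumab 5 × 16.5 = 82.5 days; brodalumab 5 × 10.9 = 54.5 days; dummy 5 × 0.0 = 0 days.
- Guselkumab arm (SAP 1.2): guselkumab at Weeks 0, 4, 12, 20; dummy 2 at Weeks 0, 1, 2, 4, 6, …, 26, which is 15 visits.
- Brodalumab arm (SAP 1.2): brodalumab at those same 15 visits; dummy 1 at Weeks 0, 4, 12, 20.
- Follow-up: a completer on nominal visit days with last contact at Week 28, so 28 × 7 = 196 days counted from the first dose.

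**Dummy-only visits**

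In the guselkumab arm, 15 − 4 = 11 visits have a dummy and no active drug: Weeks 1, 2, 6, 8, 10, 14, 16, 18, 22, 24 and 26. In the brodalumab arm every dummy 1 date is also a brodalumab date, so there are none.

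**Literal reading, same-date visits take the active product's half-life**

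Each guselkumab window is cut at the next dummy-only visit:

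- Week 0 to Week 1: Days 0–7, 7 days
- Week 4 to Week 6: Days 28–42, 14 days
- Week 12 to Week 14: Days 84–98, 14 days
- Week 20 to Week 22: Days 140–154, 14 days

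Sum: 7 + 14 + 14 + 14 = 49 days, which is 49 / 196 = 25%, or 7.0 weeks.

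For brodalumab, the longest gap between doses is 14 days, below 54.5. The last window runs to Day 182 + 54.5 = 236.5 and is cut at Day 196. Exposure is 196 of 196 days.

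**Literal reading, same-date visits take the dummy's half-life**

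Guselkumab: every active dose shares its date with a dummy, so exposure is 0 days. Brodalumab: the intervals after Weeks 0, 4, 12 and 20 are lost, 7 + 14 + 14 + 14 = 49 days, leaving 196 − 49 = 147 days.

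**Per-product reading: a dummy adds 0 days and cancels nothing**

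Guselkumab: the gaps between active doses are 28, 56 and 56 days, all below 82.5. The last window runs to Day 140 + 82.5 = 222.5 and is cut at Day 196. Exposure is 196 days. Brodalumab: 196 days, as before.

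| Reading | Guselkumab completer | Brodalumab completer |
|---|---|---|
| Literal, active half-life on shared dates | 49 days (< 16 weeks) | 196 days (> 24 weeks) |
| Literal, dummy half-life on shared dates | 0 days (< 16 weeks) | 147 days (16–24 weeks; 147 / 7 = 21) |
| Per product | 196 days (> 24 weeks) | 196 days (> 24 weeks) |

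Under the first row, an adverse event starting in the other 196 − 49 = 147 days would drop out of the guselkumab 'while exposed to IMP' table.

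**The case against.** The strongest reply is that nobody would program the rule that way. Panel 8 assigns a half-life to each product and justifies 0.0 days by the absence of active substance. The natural sense is that a dummy contributes no exposure, not that it wipes out guselkumab already given. The exposure categories also only make sense if exposure is close to continuous, because the literal rule would put every guselkumab completer in the lowest one. SAP 1 places derivation rules in the ADRG and define.xml, which may settle the matter and are not available here. This stands as evidence of intent. It does not supply the missing words: SAP 1 also aims for enough detail to reproduce the analyses, and the sentence as printed yields 0, 49 or 196 days for the same subject. The SAP gives same-date rules elsewhere (5.3, 5.4.1.2.3, 5.4.2.1) but none here.

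Some stronger inferences should be resisted:

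- A reader might infer that guselkumab subjects leave the window at every dummy injection. At Weeks 0, 4, 12 and 20 guselkumab is given on the same date; the exits from the window are at Weeks 1, 6, 14 and 22.
- A reader might infer that every reading is wrong for one arm, adding one in which guselkumab's 82.5 days run from a later dummy date. That contradicts Panel 8, which gives the dummy 0.0 days, and it would not change completers. The per-product reading is right for both arms.
- A reader might infer that the safety comparison as a whole is compromised. Treatment emergence is set by onset or worsening after the first IMP, not by this window. The adverse event, AESI, C-SSRS and PHQ-8 summaries also have a version covering the whole time in the trial, and patient-years of observation are reported beside exposure.

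**Conclusion.** The definition is wrong as written and needs correcting, although its intent can be guessed. Followed literally, it gives a guselkumab completer 49 of 196 exposed days and a brodalumab completer 196 of 196. That 4:1 ratio per completer does not depend on the number randomised. It assumes nominal visit days, last contact at Week 28, and the active product's half-life on shared dates; the opposite convention gives 0 and 147 days, so the unstated convention matters too.

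The documents do not show that the analysis will lose this time. The probable intention gives 196 days in both arms. The finding is an ambiguity whose literal resolution is absurd and falls mainly on one arm. It reaches the exposure summary and the 'while exposed to IMP' tables, and leaves the 'while in trial' tables and patient-years of observation untouched.

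**What to change.** In SAP 5.2 and 5.6.1, run the window from *the most recent date of administration of active IMP (brodalumab or guselkumab), using that product's half-life in Panel 8*. Add one sentence stating that dummy injections neither start, extend nor end an exposure window. This also settles visits at which active drug and dummy share a date. The dummy rows in Panel 8 may stay.

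Apply the same window to adverse events, AESIs, C-SSRS, PHQ-8 and patient-years of exposure. Because protocol 14.3.9.1 has the same definition, record the clarification in SAP Panel 22, and check that the ADRG and define.xml agree with it.

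The cost is one phrase in two sections, one added sentence, one Panel 22 entry and one derivation to confirm. No new data are needed. If the programming already follows the per-product reading, no result changes.

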5.3 Intercurrent events

An intercurrent event refers to a post-randomisation event that either precludes the existence of or affects the interpretation of the measurements of an endpoint. For the purposes of this trial, we define the following 3 intercurrent events:

- **Permanent discontinuation of IMP independent of pandemic restrictions:** This event occurs when a subject permanently discontinues IMP for reasons not related to COVID-19 pandemic restrictions. Permanent discontinuation of IMP due to sickness with COVID-19 (an AE) will be interpreted as permanent discontinuation of IMP independent of pandemic restrictions. This event can occur either at the subject's own initiative or at the investigator's or sponsor's discretion.

Derivation of events from data: This event will be taken to have occurred if the data recorded in the 'End of treatment' eCRF form fulfil all of the following.

- 'Has the subject completed the treatment period?' is answered 'No'
- 'Primary reason for permanent discontinuation from IMP?' is not answered 'Death' or 'Lost to follow-up'
- 'Was the decision to permanently discontinue IMP related to COVID-19 pandemic restrictions?' is not answered 'Yes'.

The timing of the event will be taken as the reported 'Date of last administration of IMP'.

- **Permanent discontinuation of IMP due to pandemic restrictions:** This event occurs when a subject permanently discontinues IMP for reasons related to COVID-19 pandemic restrictions. Permanent discontinuation of IMP due to sickness with COVID-19 (an AE) will not be interpreted as permanent discontinuation of IMP due to COVID-19 pandemic restrictions. Examples of permanent discontinuation of IMP due to pandemic restrictions

THIS DOCUMENT CONTAINS CONFIDENTIAL INFORMATION AND MUST NOT BE COPIED OR MADE AVAILABLE TO ANY THIRD PARTY WITHOUT THE PRIOR WRITTEN CONSENT OF THE LEO PHARMA GROUP

are quarantines, travel limitations, subject being unable or unwilling to travel to site due to personal pandemic-related reasons, site closures, reduced availability of site staff, and interruptions to supply chain of IMP.

Derivation of events from data: This event will be taken to have occurred if the data recorded in the ‘End of treatment’ eCRF form fulfil all of the following.

- ‘Has the subject completed the treatment period?’ is answered ‘No’
- ‘Primary reason for permanent discontinuation from IMP?’ is not answered ‘Death’ or ‘Lost to follow-up’
- ‘Was the decision to permanently discontinue IMP related to COVID-19 pandemic restrictions?’ is answered ‘Yes’.

The timing of the event will be taken as the reported ‘Date of last administration of IMP’.

- **Unblinding of subject:** This event occurs at the first instance of either

- I) Subject self-injecting IMP at home as part of the COVID-19 pandemic contingency plan (CTP Appendix 6), or
- II) Subject becoming accidentally unblinded.

Derivation of events from data: I) will be taken to have occurred at (scheduled or unscheduled) visits fulfilling both conditions,

- ‘Type of visit’ is answered ‘Remote visit due to COVID-19 pandemic restrictions’ in the ‘Visit’ or ‘Visit (Unscheduled)’ form
- ‘Number IMP(s) dispensed according to IRT system’ is not answered ‘0’ in the ‘IMP Compliance, Dispensation and Administration’ form.

II) will be taken to have occurred when unblinding of a subject is reported for a visit in a protocol deviation. Instances of II) will be identified by evaluating the descriptions for all the trial’s protocol deviations.

[figure not shown]
THIS DOCUMENT CONTAINS CONFIDENTIAL INFORMATION AND MUST NOT BE COPIED OR MADE AVAILABLE TO ANY THIRD PARTY WITHOUT THE PRIOR WRITTEN CONSENT OF THE LEO PHARMA GROUP

The timing of the intercurrent event will be taken as the earliest 'Visit date' where either I) or II) has occurred.

Note, there is a distinction between permanent discontinuation of IMP (an intercurrent event) and withdrawal from trial and/or loss to follow-up. Withdrawal from trial and loss to follow-up, which are not intercurrent events, will be addressed when specifying methods and/or assumptions for handling missing data. The death of a subject has not been described above as an intercurrent event since occurrences of this event are considered unlikely in the setting of this trial. Should it happen that a subject dies, then analyses will handle this using the same strategy as described below for addressing permanent discontinuation of IMP due to pandemic restrictions.

Journeys of 4 subjects from randomisation to primary endpoint visit are illustrated in [Panel 9](#).

Panel 9: Examples of subject journeys with respect to intercurrent events

Notes: Subject 1 completes the treatment period, subject 2 permanently discontinues IMP independent of pandemic restrictions, subject 3 permanently discontinues IMP due to pandemic restrictions, while subject 4 becomes unblinded and subsequently permanently discontinues IMP independently of pandemic restrictions.

Depending on the estimand strategy selected, the occurrence of an intercurrent event may be ignored, lead to exclusion of data observed after the occurrence of the event, become a component in the definition of the endpoint, or restrict the relevant observation window to the time prior to the occurrence of the intercurrent event. Unblinding and permanent discontinuation of IMP – either independent of pandemic restrictions or due to pandemic restrictions – may occur to the same subject. If these intercurrent events occur on the same date, permanent discontinuation of IMP will be assumed to have occurred first. If an intercurrent event occurs on

THIS DOCUMENT CONTAINS CONFIDENTIAL INFORMATION AND MUST NOT BE COPIED OR MADE AVAILABLE TO ANY THIRD PARTY WITHOUT THE PRIOR WRITTEN CONSENT OF THE LEO PHARMA GROUP

the same date as an endpoint assessment the endpoint assessment will be assumed to have occurred first.

The number and percentage of subjects experiencing intercurrent events will be summarised by visit week interval for each treatment group.

